4 GENERAL STRATEGIES FOR DATA PRESENTATION

Data with qualifiers (e.g., “<”) will be listed with the qualifier but summarized without the qualifier. Subject data listings will include data collected for all subjects. Listings will be sorted by treatment, site, subject number, nominal visit, date and time (as applicable), unless otherwise indicated.

Categorical analyses will be summarized using counts and percentages. Percentages will be based on the number of subjects in the analysis set for whom there are non-missing data, unless otherwise specified. Continuous variables, including change from baseline, will be summarized using descriptive statistics [n, mean, standard deviation (SD), median, minimum, maximum].

All statistical comparisons will be performed using two-sided tests at $\alpha=0.05$ significance level, unless specifically stated otherwise. P-values will be presented to four decimal places. P-values <0.0001 will be presented as “< 0.0001.”

All analyses will be performed using SAS v 9.3 or higher (SAS Institute, Inc, Cary, North Carolina, USA). Validation and quality control of the tables, listings and figures (TLFs) will follow the appropriate [REDACTED] standard operating procedures (SOPs).

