4.4 Multiplicity

No multiplicity adjustments will be made to any alpha levels used for statistical testing for efficacy endpoints. P-values < 0.05 at the interim analysis were used as an indication of treatment effect for all efficacy endpoints. P-values for all subsequent analyses performed are considered nominal, without conclusions drawn about statistical significance levels.

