The following analyses are post-hoc. The additional efficacy analyses outlined below were deemed necessary to assess the robustness of inferences from the pre-specified analyses to violations of the normality assumptions in the pre-specified analyses that arose from the smaller-than-planned sample size. For completeness, this Addendum reinstates multiple protocol-specified endpoints previously removed from the final analysis via the Final SAP v3.0. In addition, Adverse Event and cardiac and steroid medication summaries and listings are further detailed in this Addendum.

2. Efficacy Analyses

A parametric linear mixed effects model for repeated measures (MMRM) is the pre-specified analysis for all primary, secondary, and exploratory endpoints of the study. The original study and statistical analysis plan anticipate a total sample size of around 80 subjects. However, the final number of subjects enrolled in the study is 20. Because of the smaller sample size, the primary analysis model is less likely to be robust to departures for certain assumptions¹. Beyond simply identifying if violations of assumptions exist, a critical aspect of model checking is to understand the consequences violations (if present) had on data interpretations².

Specifically, the smaller than intended sample size necessitates increased scrutiny on the assumption of the normality of residuals in the pre-specified primary, parametric MMRM analysis. Concern regarding robustness to departures from normality of the residuals supports the use of additional analyses to supplement the pre-specified model in the HOPE-2 trial.

A common method for dealing with non-normality in a study with less than 30 subjects is to employ a non-parametric test¹. Non-parametric models generally require fewer assumptions than parametric models and therefore inferences from non-parametric models are less dependent on assumptions^{1,2}. However, parametric analyses generally have more power if assumptions are valid, which is also an important consideration when sample size is small. Data transformations can be used to alter the original distribution into a transformed distribution for which the normality assumption is more likely to be valid with small sample sizes while retaining use of a parametric model. Therefore, a data transformation can be used to satisfy normality assumptions without the loss of power inherent to non-parametric methods.

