2.2. Details of the Data Transformed Model

The primary efficacy analysis is change from baseline to Month 12 in the mid-level (elbow) dimension of the PUL 1.2 assessed via a parametric linear MMRM model to compare treatment groups in mean change from baseline to Month 12. If non-normality of the residuals is identified via the procedure identified in Section 2, a data transformation will be applied and then the primary MMRM model will be applied to the transformed data. This primary MMRM model on the transformed data tests the same hypotheses.

$$\begin{aligned} H_0: \mu_C - \mu_P &= 0 \\ H_a: \mu_C - \mu_P &\neq 0 \end{aligned}$$

where μ_C and μ_P are population mean of changes from baseline in CAP-1002- and placebo-treated subjects, respectively, which on the transformed data is also a test of the medians because the mean and the median of a distribution of percentiles are the same.

To implement this model, an MMRM analysis will be used to analyze the percentile ranked primary efficacy endpoint data using the same pre-specified ITT population. Data from the post-baseline visits (Month 3, 6, 9 and 12) will be modelled with visit, treatment, and treatment-by-visit interaction as the main effects, and ranked baseline score, site and binary stratification of entry item score of the PUL 1.2 at screening (2, 3 vs. 4, 5) as covariates. A First Order Autoregressive (AR(1)) covariance structure will be used to model the within-subject errors. The Kenward-Roger's (K-R) approximation will be used to estimate the denominator degrees of freedom. The primary comparison will be the contrast between CAP-1002 and placebo at Month 12.

For a given outcome, this analysis will be implemented by calculating the percentile rank of each change-from-baseline value relative to all observed change-from-baseline values for that outcome (across all subjects and all post-baseline observation times). The percentile ranked change-from-baseline is the dependent variable in the model.

This modeling approach will be applied to primary, secondary, and some exploratory endpoints for the ITT Population only.

In addition, for PUL and Cardiac MRI outcomes, Global Statistical Tests³ (GST) will be calculated as the averaged percentile ranked change-from-baseline.

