2.3.1. Permutation Test

Permutation tests at each analysis Visit (Month 3, 6, 9, and 12) will also be conducted as a non-parametric test for assessing robustness of the primary MMRM result. Permutation tests will be conducted by randomly sampling (without replacement) all possible permutations of the $N_{p,t}$ and $N_{T,t}$ values of the outcome variable, where $N_{p,t}$, $N_{T,t}$ are the number of subjects in placebo and treatment, respectively, at time t . The p-value is the proportion of permuted samples that have a test statistic larger than that of the observed data.

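### The post-hoc permutation p-value counts only statistics strictly larger than the observed one, so it falls below the valid permutation p when the statistic ties (minor)

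*SAP*

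**What the plan says.** The Addendum opens with "The following analyses are post-hoc". Section 2.3.1 then adds a permutation test at Months 3, 6, 9 and 12 as a "non-parametric test for assessing robustness of the primary MMRM result". Permuted data sets come from "randomly sampling (without replacement) all possible permutations" of the outcome values in the two arms at that visit, and the p-value is defined by: "The p-value is the proportion of permuted samples that have a test statistic larger than that of the observed data".

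The section does not name the test statistic, say whether raw or percentile-ranked changes are permuted, give the number of permutations, or restrict the permutation to randomisation strata. Three general rules bear on it:

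- SAP section 4 settles sidedness: "All statistical comparisons will be performed using two-sided tests". It also sets the display rule: "P-values <0.0001 will be presented as" a less-than entry.
- SAP section 4.4 sets the status of anything after the interim analysis: "P-values for all subsequent analyses performed are considered nominal".
- SAP section 3.1 stratifies randomisation by site and by PUL entry score (2 or 3 against 4 or 5).

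No section mentions ties, the observed arrangement or a plus-one correction.

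**The concern.** Under the null hypothesis the observed arrangement is one of the equally likely arrangements, so it belongs in the count, together with every other arrangement that gives the same statistic. A strict count leaves all of these out. The result lies below the valid p from the same scheme and can be exactly zero.

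Without ties the omission is trivial: one arrangement among the 184,756 possible at 10 v 10. It matters when many arrangements share the observed value of the statistic. That happens with a raw mean difference on whole-number scores in 20 subjects.

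Two things are at stake. The check can print a p on the other side of 0.05 from the valid one. A strict count of zero from a modest number of sampled permutations would also print as below 0.0001, a precision that the sample cannot support.

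**Working it through.** **Plan's own figure.** None. The documents give no permutation p, no error rate and no number of permutations.

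**Inputs from the documents.** 20 randomised subjects at 1:1 (SAP 3.1); two-sided 0.05 (SAP 4); two sites with a single subject and three with one subject in each arm (Addendum 2.3.2); ranking "across all subjects and all post-baseline observation times" (Addendum 2.2).

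**Assumptions.** Whole-number change scores; residual SD 1 to 4 points; site sizes 1, 1, 2, 2, 2, 4, 4, 4; site SD 0, 0.5 or 1 times the residual SD; correlation 0.7 between adjacent visits (AR(1)) for the ranked version. No effect of the entry-score stratum on outcome was simulated.

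**1. Worked example (constructed data).** Arm A: 2, 1, 0, 0, -1, -1, -1, -2, -3, -4 (sum -9, mean -0.9). Arm B: 0, -1, -1, -2, -2, -3, -3, -4, -4, -5 (sum -25, mean -2.5). The difference is 1.6 and the pooled SD is 1.69. All C(20,10) = 184,756 splits were enumerated, using the absolute mean difference:

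- strictly larger: 6,456, so the written p = 6,456/184,756 = 0.035
- at least as large: 12,222, so the valid p = 12,222/184,756 = 0.066
- tied with the observed value: 12,222 - 6,456 = 5,766, so the gap is 5,766/184,756 = 0.031

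**2. Size of the shortfall.** Null trials were simulated with treatment randomised within site and all splits enumerated (sampled splits for the adjusted contrast). Median of valid p minus written p, where the valid p is 0.02 to 0.15:

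| Statistic | SD 1 | SD 2 | SD 4 |
|---|---|---|---|
| Raw mean difference | 0.038-0.046 | 0.024-0.027 | 0.010-0.015 |
| Changes ranked over all visits | 0.007-0.015 | not tabulated | 0.001-0.002 |

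For a contrast adjusted for baseline and entry stratum, the shortfall is 0.0002-0.0006 over these SDs.

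The raw figures pool arm sizes of 9 v 11, 10 v 10 and 11 v 9. Separate runs without a site effect show that equal arms tie more. At SD 1, 2 and 4 the median gap was 0.050-0.064, 0.036-0.039 and 0.019-0.020 at 10 v 10, against 0.037-0.038, 0.022-0.023 and 0.011-0.012 at 9 v 11.

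**3. Type I error at nominal 0.05, raw mean difference.**

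| Site SD / residual SD | Strictly larger | At least as large | Verdict changes per 100 null trials |
|---|---|---|---|
| 0 | 0.053-0.079 | 0.028-0.046 | 1.1-4.4 |
| 0.5 | 0.043-0.055 | 0.020-0.037 | 0.7-3.5 |
| 1 | 0.016-0.028 | 0.006-0.017 | 0.2-1.8 |

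The Monte Carlo standard error is 0.002 to 0.006. With no site effect, the ranked version gives 0.047-0.059 against 0.038-0.051, and the adjusted contrast 0.044-0.063 against 0.043-0.063.

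**4. Independent check.** An exact calculation for fully exchangeable subjects at 10 v 10 gave average two-sided error for the strict rule of 0.092, 0.069 and 0.058 at SD 1, 2 and 4, against 0.029, 0.037 and 0.043 with ties counted. With ten strata of two, SD 4 and free permutation, the strict rule's error fell from 0.059 to 0.014 as the strata explained 0 to 50% of the variance.

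**5. Display.** With B sampled permutations the smallest valid p is 1/(B + 1). At B = 1,000 this is 1/1,001 = 0.0010. For any B up to 9,999 it is 0.0001 or more, yet a strict count of zero would print as below 0.0001.

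**The case against.** The best defence is that the sentence is loose wording for a count of results as extreme or more so, and the program used is not shown. That may be so. The text still defines the p-value, and nothing else in the SAP corrects it.

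Second, a material gap needs a raw, unadjusted difference on whole-number scores, and the documents state neither. The test is meant to check an MMRM that adjusts for baseline, site and entry stratum. A permuted model contrast is an equally open reading, and with it the gap all but vanishes. This stands, and it limits the size of the point. The 10 v 10 example is also the layout most prone to ties.

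Third, correcting the count can move the error rate further below 0.05. With site SD half the residual SD, the written rule gives 0.043-0.055 and the corrected rule 0.020-0.037. In the worked example an ordinary t-test gives p = 0.048, nearer to 0.035 than to 0.066. This also stands. But it arises from permuting across strata, and two departures that happen to offset each other do not make a valid p-value.

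Fourth, the display issue needs a small B and a zero count. If all splits are enumerated at 10 v 10, the smallest valid p is at most 2/184,756 = 0.00001, and the less-than entry is then correct.

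Last, the analysis is post hoc, covers one endpoint, and carries nominal p-values.

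**Conclusion.** The point holds, and it is minor. Followed as written, the rule gives a p-value below the valid permutation p from the same scheme. That direction is certain under full enumeration. The size is not: about 0.01 to 0.05 for a raw mean difference on whole-number scores (pooled arm sizes, SD 1 to 4, all assumed), at most about 0.015 for changes ranked over all visits, and under 0.001 for an adjusted contrast.

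Inflation of the overall type I error is not shown. It depends on how prognostic site is, which the documents do not give, and the strict rule's simulated error rates for a raw difference run from 0.016 to 0.079. No trial conclusion depends on this test. The practical risk is a robustness check that reads more favourably than it should when p is near 0.05.

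**What to change.** In Addendum 2.3.1:

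- State whether raw or percentile-ranked changes are permuted.
- Name the statistic, for example the absolute treatment difference at each of Months 3, 6, 9 and 12.
- Define p = (1 + number of permutations with a statistic at least as large as observed)/(B + 1) and state B. Alternatively, enumerate every split and count those at least as large (184,756 splits at 10 v 10).
- Optionally, add a version permuted within pooled site, because free permutation with the corrected count is conservative if site matters.

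The cost is a few lines of code, or one line of text if the program already counts ties. For a raw difference the p-value becomes somewhat larger, and where site is prognostic an already conservative test becomes more so. An adjusted contrast is practically unchanged.

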2.3.2. Study Site

An additional issue related to the smaller than originally intended sample size is the number of subjects per site. Ideally, there should be at least two subjects per site per treatment at each post baseline visit in order to cleanly estimate the site effect and the treatment effect along with the uncertainty / inconsistency in those effects. If the number of observations falls below this threshold, the treatment and site effects become (partially) confounded and treatment effect estimates may be biased.

In the smaller than planned HOPE-2 study, two sites have only 1 subject, and 3 sites have only 1 subject per arm. Therefore, confounding and the resulting potential bias in the estimated treatment effect is a concern. Two sensitivity models will be performed to assess the effect from this potential confounding. Each change detailed below will be implemented in the non-parametric model described above.

1. Site will be pooled until there were at least 2 subjects per pooled site per treatment arm. This will be achieved by starting with the site(s) with the fewest subjects and pooling with the next largest site(s) until the criterion is achieved.
2. Site will be removed from the model.

2.3.3. Outlier Removal

In addition to conducting the non-parametric analyses, outlier (unusual) observations that are driving the non-normality can be removed so that the normality assumptions of the pre-specified parametric model hold. After removal of the outlier subject(s) from the data, the residuals can be reassessed for normality both graphically and inferentially via the Shapiro-Wilk Test.

Although outlier removal can be a useful sensitivity analysis, it is not usually an appropriate primary approach because it violates the intention-to-treat principle that is central to unbiased assessment and is a focus of ICH E9 statistical guidance. Removing just one subject in this small

sample would remove 5% of the data and is therefore deemed less useful than non-parametric analyses, especially given that no a priori cut off for identifying outliers was pre-specified.

2.3.4. *Imputation of Missing Data*

The selected endpoints to be evaluated using imputation of missing data are as follows:

- change from baseline for the mid-level (elbow) dimension of the PUL 1.2 at Months 3, 6, 9, and 12
- change from baseline for the combined high-level (shoulder), mid-level (elbow), and distal-level (hand and wrist) dimensions of the PUL 2.0 at Months 3, 6, 9, and 12
- change from baseline for LVEF as assessed by cardiac MRI at Months 3, 6, 9, and 12

The sensitivity of the analysis of the selected endpoints above to missing data will be evaluated in the ITT population using two different techniques to impute that missing data:

1. Last z-score carried forward
and
2. Multiple imputation with 500 replicates using control-based pattern imputation for monotone missing data

To implement the first method, z-scores will be calculated by visit using all raw observed values at that visit prior to carrying the last available z-score forward to any missing data points. Once all missing data is imputed with the last available z-score, change from baseline in raw z-score will be calculated and analyzed using the primary MMRM, and percentile ranked change from baseline in raw z-score will be calculated and analyzed using the primary MMRM.

Subjects who do not have data for an intermediate visit but do have data for subsequent visits may reasonably follow the same trajectory as subjects in their respective arm, but subjects who discontinue treatment may follow the same trajectory as placebo-arm subjects. To use this reasoning with multiple imputation, intermediate missing data will first be imputed with random sampling using non-missing data from that subject's respective treatment arm so the resulting missing data pattern will be monotone. The remaining missing data will then be imputed with random sampling from non-missing placebo arm data. Once all missing data is imputed, change from baseline will be calculated and analyzed using the primary MMRM, and percentile ranked change from baseline will be calculated and analyzed using the primary MMRM.

2.3.5. *Additional Transformations*

The sensitivity of the analysis of change from baseline for the mid-level (elbow) dimension of the PUL 1.2 at Months 3, 6, 9, and 12 to data transformations will be evaluated in the ITT population using two additional data transformation methods on the raw baseline and change from baseline values:

1. Ordinal ranking
and
2. Cube-root transformation

Once the data is transformed using the above methods, the transformed values will be analyzed using the primary MMRM.

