12. Planned or anticipated thoracic or spinal surgery within the 12 months following randomization
13. Planned or anticipated lower extremity surgery within the 12 months following randomization, if ambulatory
14. Known hypersensitivity to dimethyl sulfoxide (DMSO) or bovine products
15. Initiation of treatment with metformin or insulin within 3 months prior to randomization
16. Initiation of treatment with an FDA-approved exon skipping therapy for the treatment of DMD within 24 months prior to randomization or dose adjustments to the therapy within 12 months prior to randomization with the exception of weight-based dose adjustments
17. Treatment with human growth hormone (HGH) within 3 months prior to randomization, unless on a stable dose (as determined by the site PI) for at least 24 months prior to randomization
18. Treatment with idebenone within 3 months prior to randomization
19. Treatment with a cell therapy product within 12 months prior to randomization

20. Treatment with an investigational product within 6 months prior to randomization
21. History, or current use, of drugs or alcohol that could impair their ability to comply with participation in the trial
22. Inability to comply with the investigational plan and follow-up visit schedule for any reason, in the judgment of the investigator

Investigational Product, Dosage and Mode of Administration:

[REDACTED]

[REDACTED]

Subjects assigned to CAP-1002 will receive a total dose of 150 million CDCs per administration.

Duration of Treatment: CAP-1002 (150 million CDCs) or placebo is administered once every 3 months for a total of 4 administrations.

Duration of Trial: All subjects will be followed until 12 months post Day 1.

Criteria for evaluation:

Efficacy

The following efficacy outcome measures will be performed at Months 3, 6, 9 and 12 unless otherwise specified:

- Skeletal muscle function: PUL (1.2 and 2.0), grip strength, key and tip-to-tip pinch strength, elbow flexion strength, and, if ambulatory, NSAA
- Pulmonary function: SVC, FVC, FEV₁, PEF, MIP, MEP, PCF, and IFR

- Cardiac function and structure at Month 6 and 12 only: cardiac MRI (LV ejection fraction, end-diastolic volume, end-systolic volume, stroke volume, regional systolic wall thickening, regional wall thickness, and circumferential strain)
- Quality of Life (QOL): DMD Upper Limb Patient-Reported Outcome Measures, Pediatric Outcomes Data Collection Instrument, and DMD Lifetime Mobility Scale

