¹² Basic metabolic panel (Glucose, Sodium, Potassium, Chloride, Bicarbonate, BUN, Creatinine, Calcium), comprehensive hepatic panel (Albumin, Alkaline Phosphatase, Total Protein, ALT, AST, GGT, Direct Bilirubin, Total Bilirubin).

¹³ CBC with WBC differential, hemoglobin, hematocrit and platelet count

¹⁴ Appearance, bilirubin, color, nitrite, occult blood, pH, protein, specific gravity, glucose, ketones, RBC, and WBC. If required, microscopic analysis of sediment will be performed and reported per occurrence

¹⁵ DMD genetic testing will be available at screening for subjects who have not previously completed genetic testing or whose historical genetic results were not performed at a CLIA-certified laboratory as determined by an Investigator. The turn-around time for final results may exceed the 30-day screening window; allow 29-49 days for receipt of final test results.

¹⁶ Week 6 and Month 4.5 blood samples will only be collected at the investigative site.¹⁷ Biomarkers may include those of muscle inflammation (osteopontin); systemic inflammation (IL-1 β , IL-2, IL-6, IL-10, TNF- α , CXCL10); muscle damage (troponin I [cardiac, fast skeletal, slow skeletal], troponin T, CK-MM, CK-MB, creatine kinase [total], creatine phosphate, and creatinine); and muscle regeneration (myostatin and follistatin).

¹⁸ Collected only if separate informed consent and/or assent provided

¹⁹ Subjects will undergo cardiac MRI if they are physically capable as determined by an Investigator. Subjects that cannot complete a cardiac MRI as part of the trial will complete an echocardiogram at screening using the site's local equipment, acquisition protocol, and evaluation procedures. The reported LVEF from a local interpretation, whether it's measured via cardiac MRI or echocardiogram, will be used to assess eligibility (exclusion criterion 1).

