11.7. Cardiac MRI

Subjects will undergo cardiac MRI at the Screening, Month 6 and Month 12 visits (or, Early Termination Visit) if they are physically capable as determined by an Investigator. Subjects that complete the cardiac MRI will have sufficient attention span, ability to maintain a breath-hold, lack significant contractures that would otherwise make lying flat difficult, and fit properly within the MRI scanner.

A subject’s screening cardiac MRI case will require evaluation by a site’s radiologist using institutional procedures. The reported LVEF from the local interpretation will be used to assess eligibility (exclusion criterion 1).

It is anticipated that the duration of each MRI session will be 30-45 minutes. Acquisition parameters and techniques are specified in the MRI Imaging Manual. The site-based MRI technologists will be trained and certified in the common acquisition protocol prior to initiation of enrollment at each site. All trial images and applicable imaging data will be sent to and centrally read at an independent, central, imaging core by DMD cardiovascular MRI and imaging experts.

Subjects that cannot complete a cardiac MRI as part of the trial will complete an echocardiogram at screening using the site's local equipment, acquisition protocol, and evaluation procedures. The reported LVEF from the local interpretation will be used to assess eligibility (exclusion criterion 1).

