14.5.3. Exploratory Efficacy Endpoints

Exploratory efficacy endpoints will be change from baseline in:

- High-level (shoulder) dimension of the PUL 1.2 at Months 3, 6, 9, and 12;
- High-level (shoulder) dimensions of the PUL 2.0 at Months 3, 6, 9, and 12;
- Mid-level (elbow) dimensions of the PUL 2.0 at Months 3, 6, 9, and 12;
- Distal-level (wrist and hand) dimensions of the PUL 1.2 at Months 3, 6, 9, and 12;
- Distal-level (wrist and hand) dimensions of the PUL 2.0 at Months 3, 6, 9, and 12;
- Grip strength, absolute and percent predicted, at Months 3, 6, 9, and 12;
- Tip-to-tip pinch strength, absolute and percent predicted at Months 3, 6, 9, and 12;
- Key pinch strength, absolute and percent predicted at Months 3, 6, 9, and 12;
- Elbow flexion strength, absolute and percent predicted, at Months 3, 6, 9, and 12;
- DMD UL-PROM at Months 3, 6, 9, and 12;

- PODCI scales (subject and parent) at Months 3, 6, 9, and 12;
- DMD-LMS at Months 3, 6, 9, and 12;
- NSAA at Months 3, 6, 9, and 12;
- 10MWRT at Months 3, 6, 9, and 12;
- Incidence of loss of ambulation (10MWRT > 30 seconds) at Months 3, 6, 9, and 12;
- Pulmonary function tests (absolute and percent predicted [if available]) at Months 3, 6, 9, and 12;
- LV structure and function as assessed by cardiac MRI at Months 6 and 12;
- Biomarkers, which may include osteopontin, IL-1 β , IL-2, IL-6, IL-10, TNF- α , CXCL10, troponin I (cardiac, fast skeletal, slow skeletal), troponin T, CK-MM, CK-MB, creatine kinase (total), creatine phosphate, creatinine, myostatin, and follistatin at Months 3, 6, 9, and 12;
- Resource utilization, including hospitalizations for orthopedic injury or surgery and for pulmonary infections, over the course of the trial.

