6.3.8 Cardiac MRI

LV structure and function as assessed by cardiac MRI include the following parameters:

- LV (myocardium) mass
- LV end-systolic volume
- LV end-systolic volume index
- LV end-diastolic volume
- LV end-diastolic volume index
- LV stroke volume
- LV ejection fraction
- systolic wall thickening (anterior LV, lateral LV, inferior LV, septal LV)
- regional wall motion [dyssynchrony index, circumferential uniformity ratio estimate (CURE)]
- circumferential strain (global, anterior LV, lateral LV, inferior LV, septal LV)
- LV wall thickness
 - end-systolic wall thickness average (anterior, lateral, inferior, septal)
 - end-diastolic wall thickness average (anterior, lateral, inferior, septal)

In addition, the LV mass index (g/m²) will be calculated as

$$\text{LV Mass Index (g/m}^2\text{)} = \text{LV Mass (g)}/\text{BSA (m}^2\text{)}$$

where Body Surface Area (BSA) = 0.007184 * Height (cm)^{0.725} * Weight (kg)^{0.425}. Height and weight measurements closest to the MRI scan will be used. The standing height will be used, if provided; otherwise, the height from ulna length will be used.

All observed values will be displayed in subject listings. Observed values and changes from baseline will be summarized for all parameters except LV wall thickness.

Using the model defined in Section 6.1, the comparisons of interest will be the contrasts between CAP-1002 and placebo at Months 6 and 12 for change from baseline in all parameters except LV wall thickness.

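### SAP Addendum 2.3.4 lists LVEF for imputation at Months 3 and 9, when no cardiac MRI is scheduled; restrict it and its imputed-data MMRM to Months 6 and 12

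*SAP*

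**What the plan says.** SAP Addendum 2.3.4 selects three endpoints for imputation: the mid-level PUL 1.2, the combined PUL 2.0 and LVEF. The LVEF entry reads "change from baseline for LVEF as assessed by cardiac MRI at Months 3, 6, 9, and 12".

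Every other statement of MRI timing differs:

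- Protocol Synopsis, criteria for evaluation: "Cardiac function and structure at Month 6 and 12 only".
- Protocol 11.7: "Subjects will undergo cardiac MRI at the Screening, Month 6 and Month 12 visits", with an early-termination scan as the alternative. Table 3 agrees.
- Protocol 14.5.3: "LV structure and function as assessed by cardiac MRI at Months 6 and 12".
- SAP 6.3.8: "contrasts between CAP-1002 and placebo at Months 6 and 12 for change from baseline in all parameters except LV wall thickness".

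Footnote 19 of Protocol Table 3 adds that "Subjects will undergo cardiac MRI if they are physically capable as determined by an Investigator", so not every subject need have scans.

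Addendum 2.3.4 gives two imputation methods. The first computes z-scores visit by visit and then proceeds by "carrying the last available z-score forward to any missing data points". The second is control-based multiple imputation with 500 replicates. Intermediate gaps are filled from the subject's own arm and the rest from placebo. After either method, the data go into the primary MMRM, both as changes and as percentile-ranked changes. SAP 6.1 defines that model on Months 3, 6, 9 and 12 with AR(1) errors and Kenward-Roger degrees of freedom.

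**The concern.** A scan that was never planned is not a missing observation in the usual sense. A program written from the bullet and from SAP 6.1 would nevertheless create LVEF rows at four visits and find two of them empty for nearly everyone.

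The filled-in values would carry no information about LVEF at those months. They would still enter a model that estimates one variance and one correlation across all visits, so they would affect the precision claimed at Month 12, where a real comparison exists. The Addendum's purpose is to test the robustness of the pre-specified inferences, and a check that overstates its own precision does not do that for LVEF.

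**Working it through.** The documents state no figure on this point, so there is nothing to reproduce. The check has three steps.

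**1. Visit count.** Listed visits: 3, 6, 9, 12 (Addendum 2.3.4). Scheduled visits: 6, 12 (Protocol 11.7 and Table 3). Unscheduled: 3 and 9. With 20 randomized subjects (SAP 3.1):

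- nominal LVEF cells as listed: 20 × 4 = 80
- cells with no planned scan: 20 × 2 = 40, or 40/80 = 50%
- cells if restricted to Months 6 and 12: 20 × 2 = 40, none empty by design

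Forty is an upper limit, because some subjects may not be able to have MRI.

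**2. What the two methods produce at Months 3 and 9.** Let z0, z6 and z12 be a subject's z-scores at baseline, Month 6 and Month 12.

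- *Carry-forward.* Month 3 takes z0, so its change is z0 − z0 = 0 for every subject with a baseline scan. Month 9 takes z6, so its change is z6 − z0, identical to Month 6.
- *Multiple imputation.* If draws are made within visit, there are no scheduled donor values at Month 3 or 9. The text does not say whether draws are within visit.

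**3. Effect on the Month 12 contrast (carry-forward method).** As a rough guide, if the model variance were a simple average over visits and Month 3 contributed nothing, the variance would be 3/4 of its proper value and the SE √0.75 = 0.87 of it. The simulations below give that or somewhat less. All correlations are assumed; the documents give none.

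*Simple model.* 1,500 null trials per setting, 10 per arm, REML AR(1), baseline covariate, no site or stratum, t cutoff with 17 df. Each cell gives mean model SE / empirical SD = ratio, then rejection at nominal 5%.

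| Assumed 6-month correlation | Four visits, as listed | Months 6 and 12 only |
|---|---|---|
| 0.6 | 0.348/0.434 = 80%; 10.2% | 0.402/0.419 = 96%; 5.8% |
| 0.8 | 0.268/0.363 = 74%; 14.1% | 0.322/0.363 = 89%; 6.9% |
| 0.9 | 0.199/0.272 = 73%; 13.1% | 0.243/0.274 = 89%; 7.2% |

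*Closer to the plan.* 1,500 null trials per setting, Kenward-Roger SE and df. Assumed correlations (baseline–M6, baseline–M12, M6–M12) are (0.7, 0.7, 0.8), (0.8, 0.7, 0.8) and (0.9, 0.85, 0.9). The site layout follows Addendum 2.3.2 for the small sites; the other 12 subjects are assumed to lie in three sites with two per arm, and the strata to split 10/10.

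| Setting | Four visits: SE/SD; rejection | Two visits: SE/SD; rejection |
|---|---|---|
| Site and stratum, 10 per arm | 87, 80, 79%; 9.3, 11.3, 10.9% | 98, 92, 91%; 5.7, 6.6, 6.3% |
| No site or stratum, 10 per arm | 84, 79, 73%; 10.5, 11.2, 15.6% | 98, 95, 88%; 5.4, 5.2, 8.0% |
| 8 or 6 scanned subjects per arm | 73–85%; 9.3–14.5% | 87–99%; 4.1–7.7% |

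Monte Carlo error is about 2 points on SE/SD and 0.5–0.9 points on rejection. A further run without site or stratum gave 75–88% and 8–14% as listed, against 91–103% and 3–7% with two visits.

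In the 10-per-arm rows of the second table, the artificial visits cost 11 to 16 points of SE (98 − 87 = 11 up to 95 − 79 = 16). They also raise the median degrees of freedom from about 13 to 22 with site, and from about 25 to 41 without. The remaining two-visit shortfall comes from the common-variance AR(1) structure.

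**The case against.** The bullet looks like a copying slip, and a careful programmer would probably notice it: there are no scheduled raw values at Months 3 or 9 from which to form z-scores, and SAP 6.3.8 already fixes the contrasts. That stands as a reason to expect little actual harm. It does not make the text right, since method 1 fills any gap and the model it feeds is defined on four visits. An early-termination scan could fall near Month 3 or 9, but the Addendum has no rule assigning it there.

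A reader might infer more than the documents support in four ways:

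- *That the percentile ranks would be filled with tied zeros and duplicates.* Addendum 2.2 ranks "across all subjects and all post-baseline observation times", but that phrase qualifies a reference set of observed changes. Addendum 2.3.4 ranks after imputation. Whether imputed values join the reference set is unsettled.
- *That the multiple imputation is biased because it draws from an arm without regard to the subject's own history.* The text names no conditioning variables, but its control-based pattern label and its reasoning in terms of trajectories suggest that conditioning is meant. The documents give no missing-data pattern from which a bias could be derived. This is missing detail, not a shown error.
- *That the primary result is compromised.* SAP 4.3 rules out imputation for the primary MMRM.
- *That 2.3.4 breaches the limit in Addendum 2.3 to the primary endpoint.* The two sentences do disagree, but the specific list plainly extends the general statement. The point is editorial.

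**Conclusion.** The concern holds for the LVEF visit list. It conflicts with the protocol schedule, the protocol endpoint list and SAP 6.3.8, and the conflict needs no simulation to establish.

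If executed as written, up to half of the nominal LVEF cells would be artificial. The carry-forward analysis would then understate its Month 12 SE (about 73–88% of the true SD) and reject a true null about 8–16% of the time. With the scheduled visits alone, the figures are about 88–103% and 3–8%. These sizes rest on assumed correlations, an assumed stratum split, a partly assumed site layout, and the premise that rows are created at Months 3 and 9.

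The consequence is limited. LVEF is exploratory, the Addendum calls its analyses post-hoc, and SAP 4.4 treats p-values after the interim analysis as nominal. The slip should be corrected, but it does not touch the primary analysis.

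**What to change.** Change the LVEF bullet in Addendum 2.3.4 to Months 6 and 12, and state that its imputed-data MMRM, raw and percentile-ranked, is fitted to those two visits only.

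As minor clarifications in the same edit:

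- confirm that the multiple imputation is done within visit and conditions on the subject's own baseline and earlier values;
- say whether imputed changes belong to the percentile-rank reference set;
- align the scope sentence in Addendum 2.3 with the endpoints that 2.3.4 names.

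The cost is a few lines of Addendum text and standard procedure options, plus a rerun of the LVEF sensitivity analysis if it was already produced on four visits. No new data are needed.
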